5.4.1.6 Nervous System Disorder (Neurologic Toxicity)

Grade	Cisplatin*
0-1	100%
2	75%**
3	0***

* Please note that the % dose administered is based on the original starting dose of cisplatin (75mg/m²).

** Patients with a grade 2 nervous system disorder (neurotoxicity) should hold all protocol treatment until recovery to grade 1 or less, then administer 75% dose. If grade 2 nervous system disorder (neurotoxicity) recurs with 75%, drug will be given at 50% upon resolution of nervous system disorder (neurotoxicity) to grade 1 or less. If grade 2 nervous system disorder (neurotoxicity) persists for 3 weeks, remove the patient from all protocol therapy.

*** Discontinue all protocol therapy for nervous system disorder (neurotoxicity) \geq grade 3.

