5.4.1.9 Grade 3 or 4 Non-Hematologic Toxicity

If patient develops grade 3 or 4 non-hematologic toxicity attributed to protocol therapy but not detailed above [excluding the following: anorexia, fatigue and fever without grade 3 or 4 neutrophil count decrease (neutropenia)] hold all therapy. Therapy can be restarted if the toxicity has resolved to < grade 1 by the time of the next treatment. Doses of all chemotherapy should then be reduced by 25% (of the dose received during the previous cycle). If carboplatin administered, reinstitute carboplatin AUC with decrease by one dose level (i.e. starting dose of AUC 6 dose reduction 1= AUC 5). If chemotherapy is held for more than 3 weeks, remove the patient from all protocol therapy.

A clinically relevant overlap in toxicity may arise between the immune-related dermatologic and cardiac toxicities attributed to nivolumab and dermatologic and cardiac toxicities attributed to etoposide. The management of overlapping toxicities should be guided by clinical judgment and an assessment of the most likely causative etiology, with special consideration given to the potential

for immune-mediated toxicities. Nivolumab administration should be delayed for toxicities as indicated in the management algorithms ([Appendix III](#)) that in the opinion of the treating physician are related to nivolumab. Please refer to Section [5.4.2.2](#).

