In places that there are differences from the algorithms regarding protocol directed drug modifications, please follow the protocol specific guidelines in this section.

Generally we strongly encourage early evaluation while withholding drug, and appropriate treatment as indicated in the management tables and event specific guidelines.

ALL OTHER EVENTS	Management/Next Dose for Nivolumab
≤ Grade 1	No change in dose
Grade 2	Hold until ≤ Grade 1 OR baseline (exceptions as noted below)
Grade 3	Off protocol therapy (exceptions as noted below)
Grade 4	Off protocol therapy
Recommended management: As clinically indicated	

- Any grade 2 drug-related uveitis or eye pain or blurred vision that does not respond to topical therapy and does not improve to Grade 1 severity within the re-treatment period OR requires systemic treatment should go off protocol treatment
- Any adverse event, laboratory abnormality, or intercurrent illness which, in the judgment of the investigator, presents a substantial clinical risk to the subject with continued study drug dosing should go off protocol treatment.
- Any grade 3 or 4 drug-related laboratory abnormality (i.e. amylase, lipase) or electrolyte abnormality, that can be managed with electrolyte replacement,

hormone replacement, insulin or that does not require treatment does not require discontinuation.

Skin Rash and Oral Lesions	Management/Next Dose for Nivolumab
≤ Grade 1	No change in dose *
Grade 2	Hold* until Grade ≤ 1 or resolved. Resume at same dose level.
Grade 3	Hold* until ≤ Grade 1. Resume at same level at investigator discretion
Grade 4	Off protocol therapy

*Patients with purpuric or bullous lesions must be evaluated for vasculitis, Steven-Johnson syndrome, TEN, and autoimmune bullous disease including oral lesions of bullous pemphigus/pemphigoid. Pruritus may occur with or without skin rash and should be treated symptomatically if there is no associated liver or GI toxicity. Note skin rash typically occurs early and may be followed by additional events particularly during steroids tapering.

Recommended management: AE management guidelines

Liver Function AST, ALT, Bilirubin	Management/Next Dose for Nivolumab
≤ Grade 1	No change in dose
Grade 2	Hold until WNL or baseline. Resume at same dose level.
Grade 3	Off protocol therapy
Grade 4	Off protocol therapy

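### Section 5.4.1.9 keeps all therapy on hold at Grade 1 after a Grade 3 rash, while the nivolumab skin table lets nivolumab resume at Grade 1; the two rules need reconciling.

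*Combined protocol and SAP*

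**What the plan says.** Section 5.4.1.9 opens with its scope: "If patient develops grade 3 or 4 non-hematologic toxicity attributed to protocol therapy but not detailed above". Anorexia, fatigue, and fever without Grade 3-4 neutropenia are excluded. For the remaining events all therapy is held. The restart condition is "Therapy can be restarted if the toxicity has resolved to < grade 1 by the time of the next treatment", and the limit on the hold is "If chemotherapy is held for more than 3 weeks, remove the patient from all protocol therapy".

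Restart rules elsewhere in section 5.4 read differently:

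- Section 5.4.1.6, for Grade 2 neurotoxicity on cisplatin: patients "should hold all protocol treatment until recovery to grade 1 or less, then administer 75% dose".
- Section 5.4.2.1, nivolumab, skin rash and oral lesions, Grade 3: "Hold* until ≤ Grade 1. Resume at same level at investigator discretion".
- Section 5.4.2.1, nivolumab, all other events, Grade 2: "Hold until ≤ Grade 1 OR baseline (exceptions as noted below". At Grade 3 the same table says "Off protocol therapy (exceptions as noted below".

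Section 5.4.2 sets a separate limit for nivolumab. It may be held for up to 12 weeks for toxicity specific to it, and chemotherapy may continue if nivolumab is stopped for that reason.

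**The concern.** Below Grade 1 means fully resolved. A patient whose toxicity improves to Grade 1 and stays there never meets the 5.4.1.9 condition. Chemotherapy stays on hold, the 3-week limit passes, and the patient leaves all protocol therapy. In Arm A that includes maintenance nivolumab, planned for up to 2 years or 50 doses in total.

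The nivolumab skin table treats the same degree of recovery from the same event as sufficient to resume. Two sites following the protocol faithfully could manage the same patient in different ways, depending on which section they opened.

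The missing baseline allowance matters because patients can enter with low-grade findings. Section 3.1.7, for example, admits patients with radiation effects resolved to Grade 1 or less. Under the literal wording, such an effect that worsened to Grade 3 on protocol therapy and then returned to its entry level would still fail 5.4.1.9.

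**Working it through.** The plan gives no figure to reproduce, so the check sets the rules side by side.

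**Step 1: what each threshold admits.** Below Grade 1 admits Grade 0 only. Grade 1 or less admits Grades 0 and 1. The two differ exactly for a patient who settles at Grade 1.

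**Step 2: grade- or baseline-based restart rules in section 5.4 outside 5.4.1.9.**

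| Rule | Event grade | Restart accepted at |
|---|---|---|
| 5.4.1.6 neurotoxicity (cisplatin) | 2 | Grade 1 or less |
| 5.4.2.1 all other events | 2 | Grade 1 or less, or baseline |
| 5.4.2.1 skin and oral lesions | 2 | Grade 1 or less |
| 5.4.2.1 skin and oral lesions | 3 | Grade 1 or less |
| 5.4.2.1 neurologic | 2 | Grade 1 or less |
| 5.4.2.1 renal | 2 | Grade 1 or less |
| 5.4.2.1 liver function | 2 | Normal or baseline |
| 5.4.2.1 diarrhea/colitis | 2 | Baseline |

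Six of the eight accept Grade 1. The other two accept it only when it is the baseline. Section 5.4.1.9 accepts neither Grade 1 nor baseline. Pneumonitis Grade 2 states no grade threshold. The hematologic, bilirubin and creatinine-clearance rules use laboratory cut-offs. None of these can be compared on this scale.

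**Step 3: which comparisons are like for like.** Section 5.4.1.9 concerns recovery from Grade 3-4. Only one row in the table follows a Grade 3 event: skin.

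**Step 4: does a rash fall under both rules?** Rash is not covered in 5.4.1.1 to 5.4.1.8, so a Grade 3 rash attributed to protocol therapy is within 5.4.1.9. It is also within the nivolumab skin table. Take an Arm A patient in cycles 1-4, with chemotherapy still due, whose Grade 3 rash recovers to Grade 1 and stays there:

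- Skin table: nivolumab may resume ("Resume at same level at investigator discretion").
- 5.4.1.9: all therapy stays on hold, and after more than 3 weeks without chemotherapy the patient is removed from all protocol therapy.

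**Step 5: other Grade 3 events.** For most of these the nivolumab tables take the patient off protocol therapy, with listed exceptions. Section 5.4.1.9 would hold and then allow restart on full resolution. Pneumonitis is an example: 5.4.1.1 to 5.4.1.8 do not cover it, so 5.4.1.9 permits restart, while the pneumonitis table ends protocol therapy at Grade 3. This mismatch runs the other way, with 5.4.1.9 the more permissive rule.

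**Step 6: does another sentence settle the order?** The second paragraph of 5.4.1.9 recognises overlapping dermatologic and cardiac toxicity and asks for clinical judgment about cause, but it sets no restart threshold. It refers to 5.4.2.2, which covers infusion reactions, not to the tables in 5.4.2.1. The precedence sentence in 5.4.2.1 ranks the protocol's own guidance above the management algorithms; it does not rank 5.4.1.9 against the 5.4.2.1 tables. Nothing says whether the 3-week chemotherapy limit or the 12-week nivolumab limit controls when an event falls under both.

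**The case against.** Several points on the other side stand.

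- **Not every other restart rule accepts Grade 1.** A reader might infer that 5.4.1.9 is alone in excluding it. The liver and diarrhea/colitis rows do not support that.
- **A stricter bar after a worse event is not in itself inconsistent.** Most of the Grade 1 rules follow Grade 2 events. At Grade 3 the neurotoxicity rule and most nivolumab rows are stricter than 5.4.1.9, because they end protocol therapy.
- **A rash attributed to nivolumab has a pathway of its own.** The protocol asks for judgment about cause and gives nivolumab-specific toxicity a 12-week limit. This narrows the conflict but does not remove it: 5.4.1.9 applies to anything attributed to protocol therapy, which includes nivolumab.
- **The skin row is permissive.** An investigator who keeps holding nivolumab breaks neither rule at first. Once chemotherapy has been held for more than 3 weeks, however, 5.4.1.9 requires removal, while the skin row and the 12-week limit would still let nivolumab continue.

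A reader might also see a timing conflict inside 5.4.1.9, between recovery by the next treatment and the 3-week limit. That reading is weak. The first is a condition for restart and the second a maximum hold, and a delayed cycle is naturally the next treatment.

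**Conclusion.** The contradiction is real but narrow. It is sharpest for a Grade 3 rash that recovers to Grade 1 in Arm A while chemotherapy is still due. There a permission in one section meets a prohibition, and then a removal, in another. Around it lies a broader mismatch: 5.4.1.9 makes no allowance for baseline, and its hold-and-restart rule does not match the nivolumab rows that end protocol therapy at Grade 3.

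This rests on reading the 5.4.1.9 threshold literally and on a rash counting as an event not detailed earlier in 5.4.1. If the hold on all therapy were read as chemotherapy only, the removal sentence would still end nivolumab, so the conflict would remain.

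No number of patients can be attached. The documents give neither the rate of qualifying events nor the share that stay at Grade 1. A reader might infer a heavier loss in one arm, but no arm-specific rate is given to support that. Patients who stop early are still followed to progression and for survival (section 5.7), and the primary analysis takes all eligible and treated patients (section 9.3). No effect on endpoint ascertainment, analysis set or power is shown. What is at stake is avoidable loss of assigned treatment and uneven practice between sites. That justifies a correction, not a change of design.

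**What to change.** Reconcile 5.4.1.9 with the tables in 5.4.2.1 and the 12-week nivolumab limit in 5.4.2. The amended text should state:

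1. which rule governs when an event falls under both 5.4.1.9 and a nivolumab table, including the Grade 3 rows that end protocol therapy;
2. the restart threshold in 5.4.1.9, and how a Grade 1 finding present at baseline is treated;
3. whether the 3-week chemotherapy limit also ends nivolumab.

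The sponsor's clinical team chooses the threshold and the precedence; this review takes no view on either. The cross-reference from 5.4.1.9 to 5.4.2.2 should be checked at the same time. The cost is a few sentences in the next amendment and a notice to sites, with no change to section 9.

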5.4.1.3 Hepatic toxicity

This table only lists Etoposide dose modifications.

Bilirubin	Etoposide*
$\leq 1.5 \times \text{ULN}$	100%
$> 1.5 - 3.0 \times \text{ULN}$	50%
$> 3.0 \times \text{ULN} - \leq 5.0 \times \text{ULN}$	30%
$> 5 \times \text{ULN}$	Hold**

* Please note that the % dose administered is based on the original starting dose of etoposide (100mg/m²).

** For bilirubin greater than 5 X ULN it is recommended not to use etoposide for that cycle but this is at the discretion of the treating physician. If holding, repeat labs on a weekly basis for up to 3 weeks until total bilirubin is $\leq 5 \times \text{ULN}$. The cisplatin and nivolumab doses should also be held if etoposide is held so that all drugs are kept on the same schedule. If bilirubin improves within 3 weeks to $\leq 5 \times \text{ULN}$, then resume treatment and use reduced dose per table above. If bilirubin does not improve to $\leq 5 \times \text{ULN}$ within 3 weeks, discontinue all protocol therapy.

A clinically relevant overlap in toxicity may arise between the immune-related hepatic toxicity attributed to nivolumab and hepatic toxicity attributed to etoposide. The management of hepatic toxicity should be guided by clinical judgment and an assessment of the most likely causative etiology, with special consideration given to the potential for immune-mediated hepatic toxicity. Nivolumab administration should be delayed for toxicities as indicated in the management algorithms ([Appendix III](#)) that in the opinion of the treating physician are related to nivolumab. Please refer to Section [5.4.2.2](#).

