5.4.2.2 Treatment of Nivolumab-Related Infusion Reactions

Since nivolumab contains only human immunoglobulin protein sequences, it is unlikely to be immunogenic and induce infusion or hypersensitivity reactions. However, if such a reaction were to occur, it might manifest with fever, chills, rigors, headache, rash, urticaria, angioedema, pruritis, arthralgias, hypo- or hypertension, bronchospasm, or other symptoms.

All Grade 3 or 4 infusion reactions should be reported as an SAE if criteria are met. Infusion reactions should be graded according to NCI CTCAE guidelines.

Treatment recommendations are provided below and may be modified based on local treatment standards and guidelines as medically appropriate:

Remain at bedside and monitor subject until recovery from symptoms

For Grade 1 symptoms: (Mild transient reaction; infusion interruption not indicated; intervention not indicated)

If clinically appropriate, infusion rate may be slowed or interrupted and restarted at 50% of the original infusion rate when symptoms resolve; if no further complications ensue after 30 minutes, the rate may be increased to 100% of the original infusion rate. Monitor patient closely.

The following prophylactic premedications are recommended for future infusions: diphenhydramine 50 mg (or equivalent, oral) and/or acetaminophen 325 to 1000 mg at least 30 minutes before additional nivolumab administrations, slowing infusion rate as above.

For Grade 2 symptoms: (Therapy or infusion interruption indicated but responds promptly to symptomatic treatment (e.g., antihistamines, NSAIDS, narcotics, IV fluids); prophylactic medications indicated for \leq 24 hrs), and no further nivolumab administration should be considered at that visit.

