Rule out non-inflammatory causes. If non-inflammatory cause, treat accordingly and continue I-O therapy. Consider imaging for obstruction.

[figure not shown]
Patients on IV steroids may be switched to an equivalent dose of oral corticosteroids (e.g. prednisone) at start of tapering or earlier, once sustained clinical improvement is observed. Lower bioavailability of oral corticosteroids should be taken into account when switching to the equivalent dose of oral corticosteroids.

*I-O therapy may be delayed rather than discontinued if AST/ALT ≤ 8 x ULN and T.bili ≤ 5 x ULN.

**The recommended starting dose for grade 4 hepatitis is 2 mg/kg/day methylprednisolone IV.

Neurological Adverse Event Management Algorithm

[figure not shown]
Rule out non-inflammatory causes. If non-inflammatory cause, treat accordingly and continue I-O therapy.

Patients on IV steroids may be switched to an equivalent dose of oral corticosteroids (e.g. prednisone) at start of tapering or earlier, once sustained clinical improvement is observed. Lower bioavailability of oral corticosteroids should be taken into account when switching to the equivalent dose of oral corticosteroids.

Pulmonary Adverse Event Management Algorithm

[figure not shown]
Rule out non-inflammatory causes. If non-inflammatory cause, treat accordingly and continue I-O therapy. Evaluate with imaging and pulmonary consultation.

Patients on IV steroids may be switched to an equivalent dose of oral corticosteroids (e.g. prednisone) at start of tapering or earlier, once sustained clinical improvement is observed. Lower bioavailability of oral corticosteroids should be taken into account when switching to the equivalent dose of oral corticosteroids.

Renal Adverse Event Management Algorithm

[figure not shown]
Rule out non-inflammatory causes. If non-inflammatory cause, treat accordingly and continue I-O therapy

Patients on IV steroids may be switched to an equivalent dose of oral corticosteroids (e.g. prednisone) at start of tapering or earlier, once sustained clinical improvement is observed. Lower bioavailability of oral corticosteroids should be taken into account when switching to the equivalent dose of oral corticosteroids.

Skin Adverse Event Management Algorithm

Rule out non-inflammatory causes. If non-inflammatory cause, treat accordingly and continue I-O therapy.

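### Sections 5.4.1.3 and 5.4.1.9 refer nivolumab-related toxicity to Appendix III and the infusion-reaction section but omit 5.4.2.1, whose hold/stop tables prevail; liver events are most affected

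*Combined protocol and SAP*

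**What the plan says.** Section 5.4.1 gives the chemotherapy dose modifications. Two of its subsections recognise that a toxicity may come from etoposide or from nivolumab.

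- **5.4.1.3 (hepatic).** For liver toxicity the physician attributes to nivolumab, the site is to delay nivolumab as Appendix III indicates. The paragraph ends with toxicities that "are related to nivolumab. Please refer to Section [5.4.2.2".
- **5.4.1.9 (other Grade 3 or 4 non-hematologic).** The same instruction covers overlapping skin and cardiac toxicity: "that in the opinion of the treating physician are related to nivolumab. Please refer to Section [5.4.2.2".
- **5.4.2.2**, the section both cite, is headed "Treatment of Nivolumab-Related Infusion Reactions". It covers infusion reactions and late hypersensitivity and has no organ-specific hold/stop table.
- **5.4.2.1** has those tables and states their rank: "In places that there are differences from the algorithms regarding protocol directed drug modifications, please follow the protocol specific guidelines in this section". Its liver table takes Grade 3 and Grade 4 events off protocol therapy. The one row with a hold and restart is Grade 2: "Hold until WNL or baseline. Resume at same dose level".
- **Appendix III**, in a footnote to the hepatic algorithm: "I-O therapy may be delayed rather than discontinued if AST/ALT ≤ 8 x ULN and T.bili ≤ 5 x ULN".
- **5.4.1.3, bilirubin footnote**, for bilirubin above 5 x ULN, on the other drugs: "The cisplatin and nivolumab doses should also be held if etoposide is held so that all drugs are kept on the same schedule". Should the value then fall to 5 x ULN or below within 3 weeks, "then resume treatment and use reduced dose per table above"; if not, all protocol therapy stops.

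**The concern.** These are operative dosing instructions for Arm A. A site that follows both printed references reads Appendix III and then infusion-reaction advice. It is not sent to the tables that decide whether nivolumab is held or stopped, or to the sentence that makes those tables prevail. For liver events the printed path can look complete while giving a more lenient answer than 5.4.2.1, so a site could delay and resume nivolumab where the governing table requires stopping. The liver section of 5.4.2.1 itself warns that dosing through active immune-mediated hepatitis may worsen the inflammation. What is at stake is patient safety and uniform conduct of Arm A.

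**Working it through.** The plan states no figure to reproduce. The check traces the references, compares the rules, and sizes the disagreement.

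**1. References.** Two subsections of 5.4.1 (5.4.1.3 and 5.4.1.9) direct nivolumab-related toxicity elsewhere. Both name Appendix III and 5.4.2.2, and neither names 5.4.2.1.

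**2. Liver rules compared.**

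| Situation, event judged nivolumab-related | Path as printed | 5.4.2.1 liver table |
|---|---|---|
| Grade 3, AST/ALT at most 8 x ULN and bilirubin at most 5 x ULN | Appendix III: nivolumab may be delayed | Off protocol therapy |
| Bilirubin above 5 x ULN, falling to 5 x ULN or less within 3 weeks | 5.4.1.3 footnote: nivolumab held with etoposide, then treatment resumes | Off protocol therapy if Grade 3 or 4 |

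Section 5.4.2.1 also exempts some Grade 3 or 4 laboratory abnormalities from discontinuation. That exemption is listed under the table for all other events. The liver has its own table, which carries no exemption.

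**3. Size of the Appendix III disagreement.** The documents do not print the CTCAE cut-offs, so let Grade 3 start above *g* x ULN. The two rules differ from *g* up to the Appendix III limit, provided the other measure is also within its limit.

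- AST/ALT, width 8 − *g*. Assumed *g* = 5: 8 − 5 = 3 x ULN. Range: *g* = 3 gives 8 − 3 = 5; *g* = 8 gives 8 − 8 = 0.
- Bilirubin, width 5 − *g*. Assumed *g* = 3: 5 − 3 = 2 x ULN. Range: *g* = 1.5 gives 5 − 1.5 = 3.5; *g* = 5 gives 5 − 5 = 0.

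The central values assume a normal baseline. Section 3.1.5 admits AST/ALT up to 3 x ULN, or up to 5 x ULN with known liver metastases. If grading were relative to a raised baseline, *g* in ULN multiples would be higher and the AST/ALT band narrower.

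**4. Bilirubin footnote.** Here the difference does not come from Appendix III, whose delay option ends at 5 x ULN. It comes from the footnote, which names nivolumab in the hold and does not except it when treatment resumes. For every *g* in the 1.5 to 5 range, bilirubin above 5 x ULN is at least Grade 3, so the liver table offers no restart.

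**5. Restart sentence in 5.4.1.9.** For Grade 3 or 4 toxicity attributed to protocol therapy, all therapy is held and may restart once the event is below Grade 1. The sentence does not say which drugs it means. What follows is about chemotherapy: a 25% reduction, a carboplatin AUC step, and a 3-week limit on a chemotherapy hold. Section 5.4.2 sets a separate 12-week limit on holding nivolumab for its own toxicity. The sentence reads mainly as a chemotherapy rule but does not say so.

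**The case against.** The strongest reply is that the governing rule is already in the protocol and does not depend on being cited. Section 5.1 sends dose modifications to Section 5.4 as a whole. Section 5.4.2.1 is titled after the management algorithms that 5.4.1.3 and 5.4.1.9 mention, directly precedes the section they cite, and asserts its own precedence. A careful reader would find it. This stands, and it limits the severity. It does not make the references right: someone following the section number passes over the tables, and for liver events Appendix III appears to answer the question.

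It can also be said that the bilirubin footnote belongs to an etoposide table, holds nivolumab only to keep the drugs on one schedule, and can only mean etoposide when it speaks of a reduced dose. That is fair for a bilirubin rise due to chemotherapy or disease. For a nivolumab-related rise, the paragraph that should separate the cases leads to the wrong section.

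Three stronger readings are tempting, and the documents do not support them.

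- *That 5.4.1.9 contradicts 5.4.2.1 by letting nivolumab restart after Grade 3 or 4 events.* The restart sentence is permissive, is surrounded by chemotherapy instructions under a chemotherapy heading, and is followed by a separate nivolumab paragraph. Other parts of 5.4.1 do direct nivolumab holds, so a clarification is justified, but no contradiction is shown.
- *That the restart limits can be compared as 5 x ULN against normal or baseline.* The normal-or-baseline limit is in the Grade 2 row. Under the grading assumed here, that row does not apply above 5 x ULN.
- *That cardiac events should be assigned to the table for all other events.* The algorithm groups listed in 5.4.2.1 include no cardiac one, but the flow charts are not shown. Naming that table would also expressly endorse hold-and-resume at Grade 2, which is a clinical decision.

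**Conclusion.** The point holds as a cross-reference error with a safety consequence. Both references omit the section that decides nivolumab hold or stop, and for liver events the printed path is more lenient than the governing table. Under the assumed cut-offs, the Appendix III option and the liver table disagree over AST/ALT >5 to 8 x ULN and bilirubin >3 to 5 x ULN. The widths are 3 and 2 x ULN, with ranges 0 to 5 and 0 to 3.5. The footnote's resumption after bilirubin above 5 x ULN disagrees with the table across the whole range considered.

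The omission of 5.4.2.1 is certain from the text. The size of the liver bands depends on cut-offs the documents do not print. The comparison uses the printed Appendix III footnote only, since the algorithm figure is not shown. Toxicity attributed only to chemotherapy is unaffected. The documents give no rate for these events in this trial, so no patient count follows, and nothing here bears on power or type I error. The text should be corrected, but the design does not need to change.

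**What to change.** 1. In 5.4.1.3 and 5.4.1.9, cite 5.4.2.1 for decisions to hold, resume or stop nivolumab. Keep 5.4.2.2 for infusion or hypersensitivity reactions, which remain relevant to skin events, and keep Appendix III for management.
2. Add to the bilirubin footnote in 5.4.1.3: *If the hepatic toxicity is considered related to nivolumab, nivolumab is resumed only as the liver table in 5.4.2.1 allows.*
3. As a clarification, add to 5.4.1.9: *The restart sentence above governs chemotherapy. For toxicity considered related to nivolumab, resumption of nivolumab follows 5.4.2 and 5.4.2.1.*

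The cost is amendment wording: two corrected references and two short additions. No new tests, visits or staff are needed.
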